**Appendix 2            Equations and Conversion Factors**

1. Cockcroft-Gault equation to calculate creatinine clearance (CrCl) (relevant to Exclusion criterion number 26):

$$\frac{(140 - \text{age [yrs]}) * \text{weight (kg)} * (Z)}{\text{Cr (mg/dL)} * 72} \quad Z = 0.85, \text{ if Female}$$

2. Corticosteroid conversions (relevant to Exclusion criterion number 19):

The following have equivalent glucocorticoid activity a	
Hydrocortisone	160 mg
Prednisone	40 mg
Prednisolone	40 mg
Methylprednisolone	32 mg
Triamcinolone	32 mg
Dexamethasone	6 mg

a Axelrod L. Glucocorticoid therapy. In: Jameson JL & De Groot LJ, eds. Endocrinology. 6th ed. Philadelphia, PA: Saunders; 2010:1840.

Omadacycline  
PTK0796-AP-17202-Version1.0; 26Mar2018

Paratek Pharma, LLC.  
IND # 75,928 IND # 73,431

### Appendix 3                      Modified Patient Symptom Assessment Questionnaire (mPSAQ)

Pyelonephritis Symptoms	Symptom Assessment	Bothersome Assessment
	Please indicate whether you have had the symptom in the past 24 hours?	If you have experienced the symptom in the past 24 hours, please indicate how bothersome they were?
Lower back pain or flank pain	No symptom	Not at all
	Mild	A little
	Moderate	Moderately
	Severe	A lot
Chills, rigors or warmth	No symptom	Not at all
	Mild	A little
	Moderate	Moderately
	Severe	A lot
Pain or uncomfortable pressure in the lower abdomen/pelvic area	No symptom	Not at all
	Mild	A little
	Moderate	Moderately
	Severe	A lot
Pain or burning when passing urine	No symptom	Not at all
	Mild	A little
	Moderate	Moderately
	Severe	A lot
Frequency of urination or going to the toilet very often	No symptom	Not at all
	Mild	A little
	Moderate	Moderately
	Severe	A lot

Omadacycline  
PTK0796-AP-17202-Version1.0; 26Mar2018

Paratek Pharma, LLC.  
IND # 75,928 IND # 73,431

Urgency of urination or a strong and uncontrollable urge to pass urine	No symptom	Not at all
	Mild	A little
	Moderate	Moderately
	Severe	A lot

Omadacycline  
PTK0796-AP-17202-Version1.0; 26Mar2018

Paratek Pharma, LLC.  
IND # 75,928 IND # 73,431

## **Glossary of Abbreviations**

Abbreviation	Definition	
AE	Adverse event	
AP	acute pyelonephritis	
ATC	Anatomical Therapeutic Chemical Classification	
BMI	Body Mass Index	
CE	clinically evaluable	
CFU	colony forming unit	
CI	confidence interval	
CN	clinically notable	
CrCl	creatinine clearance	
DMC	Data Monitoring Committee	
DMID	Division of Microbiology and Infectious Diseases	
eCRF	electronic case report form	
EOT	end of treatment	
FFU	final follow-up	
ICF	informed consent form	
ITT	intent-to-treat	
iv	Intravenous(ly)	
IxRS	Interactive Response System	
LEV	levofloxacin	
ME	microbiologically evaluable	
MedDRA	Medical Dictionary for Regulatory Activities	
MIC	minimum inhibitory concentration	
micro-ITT	microbiological intent to treat	
mPSAQ	modified Patient Symptom Assessment Questionnaire	
N	number of subjects	
OMC	omadacycline	
РК	pharmacokinetic	
ро	oral(ly)	
РТ	preferred term	
РТЕ	Post Therapy Evaluation	
QTc	QT, corrected	

#### 293 Version: 1.0 Status: Approved Approved Date: PTK0796-AP-17202 Statistical Analysis Plan

Omadacycline (PTK 0796)

Paratek Pharma, LLC

PTK0796-AP-17202 Statistical Analysis Plan

SAP	Statistical Analysis Plan	
SD	standard deviation	
SI	International System	
SOC	system organ class	
TEAE	treatment-emergent adverse event	
ULN	upper limit of normal	
UTI	urinary tract infection	
WBC	white blood cell	

-0293 Version: 1.0 Status: Approved Approved Date: PTK0796-AP-17202 Statistical Analysis Plan

Omadacycline (PTK 0796)

Paratek Pharma, LLC

PTK0796-AP-17202 Statistical Analysis Plan

## **1 INTRODUCTION**

This Statistical Analysis Plan (SAP) describes the planned analysis and reporting for Paratek Pharma Protocol PTK0796-AP-17202 (A Randomized, Double-Blinded, Adaptive Phase 2 Study to Evaluate the Safety and Efficacy of intravenous (iv) or iv/po omadacycline and iv/po levofloxacin in the Treatment of Adults with Acute Pyelonephritis).

The reader of this SAP is encouraged to read the study protocol for details on the conduct of this study, the operational aspects of clinical assessments, and the timing for completing the participation of a patient in this study.

The SAP is intended to be in agreement with the protocol, especially with regards to the primary and all secondary endpoints and their respective analyses. However, the SAP may contain more details regarding these particular points of interest, or other types of analyses (e.g. other endpoints). When differences exist in descriptions or explanations provided in the study protocol and this SAP, the SAP prevails; the differences will be explained in the Clinical Study Report.

Methods of reporting of pharmacokinetic (PK) data are outside of scope of this SAP.

0293 Version: 1.0 Status: Approved Approved Date: PTK0796-AP-17202 Statistical Analysis Plan

Omadacycline (PTK 0796)

PTK0796-AP-17202 Statistical Analysis Plan

## 2 STUDY OBJECTIVES, ENDPOINTS, AND MEASURES

The primary objective of this study is to evaluate the efficacy of iv and iv to oral (iv/po) dosing regimens of omadacycline and levofloxacin in the treatment of adults with acute pyelonephritis (AP).

The efficacy endpoints include clinical response, microbiological response, and the composite of clinical and microbiological (overall) response, as measured by the number and percentage of subjects achieving success.

The efficacy outcomes are measured by the number and percentage of subjects with successes in the ITT, micro-ITT populations, and other populations of interest as appropriate.

The secondary objectives of this study are:

- To evaluate the safety of omadacycline in the treatment of adults with AP.
- To evaluate the PK of omadacycline in adults with AP

Methods of reporting of PK data are outside of scope of this SAP.

293 Version: 1.0 Status: Approved Approved Date: PTK0796-AP-17202 Statistical Analysis Plan

Omadacycline (PTK 0796)

Paratek Pharma, LLC

PTK0796-AP-17202 Statistical Analysis Plan

## **3 STUDY DESIGN**

This is a randomized, double-blinded, adaptive designed Phase 2 study evaluating once-daily iv or iv/po dosing regimens of omadacycline compared to one once-daily dosing regimen of iv/po levofloxacin in the treatment of adults with AP. The planned length of subject participation in the study is up to 30 days, which includes a total duration of study therapy for 7 to 10 days (iv only or iv and oral combined). Subjects with bacteremia confirmed from local blood culture drawn at screening can receive up to 14 days of treatment.

The study will consist of 3 protocol-defined phases: Screening, double-blind treatment and follow-up. All Screening evaluations should be completed within the 24 hours prior to randomization. Subjects who meet inclusion criteria, and do not meet exclusion criteria will be randomly assigned to iv or iv/po omadacycline dosing regimens or a regimen of iv/po levofloxacin (Table 1). Subjects should receive their first dose of test article at the site within 4 hours after randomization. IV and oral treatment will be double-blinded and oral treatment will be double-dummy. Please refer to Section 9 of the protocol for further details on study phases and required assessments/procedures per phase.

During the study treatment period, blood samples will be collected for safety analysis and for PK analysis of omadacycline. Blood will also be drawn during each subject's Screening evaluation for microbiologic culture; repeat samples will be taken during subsequent visits if bacteremia is identified during Screening. Urine samples will be collected during the study period for safety, PK analysis, and microbiological analysis. Safety assessments will include monitoring of adverse events (AEs), concomitant medications, clinical laboratory test results, vital sign measurements, pregnancy testing and physical examination findings.

Subject visits occur on Days 1 to 7. If treatment extends beyond 7 days, subject visits may occur on Days 8 to 10. If treatment extends beyond 10 days for subjects with bacteremia based on screening culture, visits will occur on Days 11 to 13. An end of treatment (EOT) visit will be conducted on the day of or within 2 days following the last dose of test article. Subjects will return to the study site for a Post Therapy Evaluation (PTE) on Day 21 ( $\pm$  2 days). A Final Follow-up visit (Final Follow-up) will be conducted on Day 28 ( $\pm$  2 days) following the first dose of test article. The Final Follow-up assessment may be conducted via telephone contact or by another interactive technology for subjects who were considered to be clinical successes and had no AEs or clinically significant laboratory or electrocardiogram abnormalities noted at or after the PTE visit. Otherwise, this assessment is to be performed with an in-person study visit. During the Follow up call/visit, if the subject reports symptoms of potential recurrence, additional procedures will be performed.

A study schedule of events is provided in Table 1 of the protocol.

For details regarding interim adaptive design refer to Section 3.4.

## 3.1 Sample Size Considerations

Enrollment of approximately 200 subjects is planned to achieve at least 150 subjects in the micro-ITT population. The Bayesian posterior probability that the overall success rate of the

93 Version: 1.0 Status: Approved Approved Date: PTK0796-AP-17202 Statistical Analysis Plan

Omadacycline (PTK 0796)

Paratek Pharma, LLC

PTK0796-AP-17202 Statistical Analysis Plan

composite endpoint at the PTE Visit is within 0.10 of that of the levofloxacin group will be estimated for each omadacycline treatment group. The target probability is 0.70. If the true underlying overall success rates for the levofloxacin and omadacycline treatment groups are 0.69, then the sample size of N = 30 per treatment group has approximately 65% power/probability to yield the target probability (N = 80 per treatment group for 80% power). If the true underlying overall success rates for the levofloxacin and omadacycline treatment groups are 0.78, then the sample size of N = 30 per treatment group has approximately 68% power/probability to yield the target probability (N = 64 per treatment group for 80% power). The sample size may be increased for a particular omadacycline treatment group by changing the randomization ratio and/or dropping a treatment group to have improved power/probability of achieving the target probability that overall success rates for a treatment group is within 0.10 of that of the levofloxacin group.

The decisions affecting changes of randomization to treatment groups, hence affecting total sample size, will be based on the recommendation of the Data Monitoring Committee (DMC) at interim analyses in a blinded to study team manner based on safety, and tolerability of treatments. Details are documented in the Data Monitoring Committee Charter for Phase II Trial for PTK0796-AP-17202.

### 3.2 Data Monitoring Committee

A DMC will provide ongoing monitoring of data. The charter for the DMC will outline membership, all roles, responsibilities, and decision-making criteria. This will include a detailed description of the manner in which security and blinding of the data for the study management team will be maintained, in addition to the procedures that ensure the independence and objectivity of the DMC's activities. As the DMC will be reviewing data for this study, it may require reports indicating treatment assignment to assist in clinical interpretation of its findings. Therefore, the DMC charter will provide a detailed explanation of the processes by which the DMC will obtain the information necessary for its operation that will not prejudice or create any potential source of bias in the conduct of the study.

#### 3.3 Randomization and Blinding

Initially, subjects will be randomized 1:1:1:1:1 to one of the following 5 treatment groups:

#### Omadacycline (PTK 0796)

Paratek Pharma, LLC

PTK0796-AP-17202 S	Statistical Analy	sis Plan
--------------------	-------------------	----------

	Description of freatment groups			
		Study Day	Study Days	Study Days
Group	Test Article	1	2 to 7	8 to 10 a
Group 1	omadacycline	200 mg iv	200 mg iv	200 mg iv
Group 2	omadacycline	200 mg iv	100 mg iv	100 mg iv
Group 3	omadacycline	200 mg iv	300 mg po or 100 mg iv	300 mg po or 100 mg iv
Group 4	omadacycline	200 mg iv	450 mg po or 100 mg iv	450 mg po or 100 mg iv
Group 5	levofloxacin	750 mg iv	750 mg po or 750 mg iv	750 mg po or 750 mg iv

### Table 1Description of Treatment groups

iv = intravenous, po = per oral;

Note: dosing in all treatment groups is once-per-day:aThe total duration of treatment for subjects is 7-10 days, up to 14 days of treatment for subjects with bacteremia.

All eligible subjects will be randomized via an Interactive Response System (IxRS) that assigns them to the treatment arm. The site delegate will contact the IxRS after confirming that the subject fulfills all the inclusion criteria and has none of the exclusion criteria. The IxRS will assign a test article to the subject based on a computer-generated randomization schedule. The randomization will be a blocked randomization sequence as defined in the IxRS specifications.

It is possible that not all treatment arms will be enrolling subjects at the same time. Arms may be dropped based on DMC recommendations. There will always be at least one omadacycline arm and the levofloxacin arm open.

Subjects randomized into the study will be assigned the treatment corresponding to the next available number from the computer-generated randomization schedule. The subject is considered randomized when the IxRS provides the test article assignment, regardless of whether the subject actually receives any medication. As this is an adaptive design trial, any updates to the randomization schedule based on DMC recommendation and will be incorporated into the IxRS system.

The investigator and sponsor will be blinded to treatment arm assignments. The iv and po phases of the study will be double-blind.

Because the color of the iv test article infusions and placebo infusions differ, all infusion bags and iv tubing will be covered with materials provided by the sponsor so that subjects and blinded study personnel will not know the identity of the test article being administered. The infusion regimen will follow a blinded design with subjects in each study arm receiving the same infusion volumes with the same administration instructions. Blinded study personnel will administer the infusions and collect, review and enter data regarding the iv infusions (eg, start and stop times) into an electronic case report form (eCRF). If gravity administration is not the standard of care, then an infusion pump may be used. If an infusion pump is used, then an unblinded administrator will be required. Personnel identified as unblinded administrators will not participate in any study procedures other than iv administration of test article and the collection, review and entry of iv related data (eg, start and stop times) into an eCRF.

93 Version: 1.0 Status: Approved Approved Date: PTK0796-AP-17202 Statistical Analysis Plan

Omadacycline (PTK 0796)

Paratek Pharma, LLC

## PTK0796-AP-17202 Statistical Analysis Plan

During the po phase, a double-blind, double-dummy design will be used to ensure the blind is maintained. Subjects on the omadacycline arms may receive active omadacycline tablets and over-encapsulated levofloxacin placebo tablets. Subjects on the levofloxacin arm will receive omadacycline placebo tablets and over-encapsulated active levofloxacin tablets. Infusions will be administered concomitantly along with the po treatment to maintain the overall study blind.

Data that could potentially lead to unblinding will not be accessible to anyone other than the following site personnel:

- unblinded study pharmacist or designee
- unblinded study monitor
- unblinded administrator(s)

Unblinding is only to occur in the case of subject emergencies and at the conclusion of the study.

## 3.4 Interim Analyses

This is an adaptive dose-response finding study.

Interim analyses will be conducted when data are available for approximately 40, 80 and 100 subjects in order for DMC to provide recommendation on the following:

- Omadacycline treatment group(s) that can be initiated or dropped from the trial
- Modification of the randomization ratios among the treatment groups
- Need for extension of the trial beyond 200 enrolled subjects to provide more precise estimates of the efficacy outcome

To protect the integrity of the clinical study, neither the actual randomization schedule nor the data from the data reviews will be made available to the Sponsor Study team or the Study Reporting team. Data for the unblinded data reviews by the DMC will only be released to the DMC, the independent reporting statistician, and the DMC Reporting team. For details refer to Data Monitoring Committee Charter for Phase II Trial for PTK0796-AP-17202.

Decisions on randomization re-allocation and/or dropping dose groups will be based primarily on safety and tolerability. Efficacy will only be considered for dose-reallocation if the DMC deems the response rates as too low to proceed with enrollment. Efficacy is not pre-planned with statistical decision criteria due to high variability in small sample sizes.

Based on the results of analyses during the interim reviews, the DMC may recommend continuation of enrollment above 200 subjects. The purpose of an increase in sample size, among other reasons, may be due to the need to provide more precise estimates of the efficacy outcome or for further exploration of safety and tolerability data.

## 3.5 Final Analyses and Reporting

All analyses identified in this SAP will be performed according to the study protocol, ie, after the end of study as defined in the study protocol.

293 Version: 1.0 Status: Approved Approved Date: PTK0796-AP-17202 Statistical Analysis Plan

Omadacycline (PTK 0796)

Paratek Pharma, LLC

PTK0796-AP-17202 Statistical Analysis Plan

This SAP and any corresponding amendments will be approved before database lock. The randomization codes will not be unblinded until this SAP has been approved and issued.

0293 Version: 1.0 Status: Approved Approved Date: PTK0796-AP-17202 Statistical Analysis Plan

Omadacycline (PTK 0796)

Paratek Pharma, LLC

PTK0796-AP-17202 Statistical Analysis Plan

# 4 ANALYSIS POPULATIONS

The following subject analysis populations have been defined.

## 4.1 Intent-to-treat Population

The intent-to-treat (ITT) population will consist of all randomized subjects regardless of whether or not the subject received test article.

A subject is considered randomized when the IxRS provides the test article assignment by providing the kit number (i.e., completes a randomization transaction). Subjects in this population will be summarized according to randomized test article assignment.

## 4.2 Safety Population

The Safety population will consist of all randomized subjects who receive any amount of test article. All safety analyses will be conducted in this population; subjects will be summarized according to actual test article received.

## 4.3 Microbiological ITT Population

The micro-ITT population will consist of subjects in the ITT population who have an appropriately collected pretreatment baseline urine culture with at least 1 uropathogen at  $\geq 10^5$  colony forming unit (CFU)/mL and not more than 2 bacterial isolates at any count. If more than 2 bacterial isolates are identified, the culture will be considered contaminated regardless of colony count, unless 1 of the isolates that grows in the urine at  $\geq 10^5$  CFU/mL is also isolated from a blood culture at the same visit.

Rules for Sponsor's determination of qualifying pathogens is described in the Pathogen and CE.

# 4.4 Clinically Evaluable Population

The clinically evaluable (CE) population will consist of all ITT subjects who received test article, have acute uncomplicated pyelonephritis (AP), an assessment of outcome, and meet all other evaluability criteria.

Inclusion into the CE populations will be determined programmatically based on the data on the eCRF and a manual review by the Sponsor as necessary prior to unblinding. Details on allocation to each CE population are described in the Pathogen and CE.

Since patient count may differ depending on timepoint, CE populations will be defined by milestone visit (CE-EOT, CE-PTE and CE-FFU). To be included in the populations, subjects must meet all criteria defined below:

1. Qualifying infection:

Inclusion Criterion #2: Females age 18 years or older

93 Version: 1.0 Status: Approved Approved Date: PTK0796-AP-17202 Statistical Analysis Plan

Omadacycline (PTK 0796)

Paratek Pharma, LLC

PTK0796-AP-17202 Statistical Analysis Plan

Inclusion Criterion #3: Clinical signs and symptoms of acute uncomplicated pyelonephritis with onset or worsening within 96 hours prior to randomization.

Inclusion Criterion #4: A clean-catch midstream urine sample with dipstick analysis positive (at least ++) for leukocyte esterase or pyuria (white blood cell [WBC] count >  $10/\mu$ L in unspun urine or  $\ge 10$  per high power field in spun urine sediment).

2. Assessment of Outcome for CE population:

Subjects must meet all of the following to be included in the CE populations:

- Subject did not meet one of the exclusion criteria 6 through 15 of the protocol (Baseline event exclusion)
- Received the randomized test article and was at least 80% compliant with the dosing regimen (Compliance to test article intake).
- Study personnel involved in the assessment of efficacy remained blinded to study treatment, unless a treatment limiting AE occurred which required emergency unblinding. In addition, for each endpoint the following needs to be satisfied, as appropriate:
  - a. For the CE-EOT population:
    - i. Completed the investigator's assessment of clinical response (i.e., was not deemed an indeterminate outcome) at the EOT visit, and
    - ii. The EOT visit occurred on the day of, or within  $\pm 2$  days, following the last dose of test article (3 days window).
  - b. For the CE-PTE population:
    - i. The Overall Clinical Response (based on the investigator's assessment) at the PTE Visit is not Indeterminate (see Table 5).
    - ii. The PTE Visit occurred Day 21 (± 2 days), unless the subject was considered to be a Clinical Failure based on the investigator's assessment at the EOT visit.
  - c. For the CE-FFU population:
    - i. The overall Clinical Response (based on the investigator's assessment) at the Final Follow-up (FFU) Visit is not Indeterminate.
    - ii. The FFU Visit occurred on Day 28 ( $\pm$  2 days) from the first dose of test article), unless the subject was considered to be a Clinical Failure based on the investigator's assessment at the PTE visit.
- 3. Other Evaluability Criteria
  - a. Prior Antibiotic Therapy

Exclusion Criterion #2: Receipt of any dose of a potentially therapeutic antibacterial agent (with potential activity against uropathogens in the urinary tract) from 72 hours prior to randomization until the first dose of test article. [Note: Subjects who developed the current pyelonephritis while receiving prophylactic antibacterial

93 Version: 1.0 Status: Approved Approved Date: PTK0796-AP-17202 Statistical Analysis Plan

Omadacycline (PTK 0796)

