## 7.11 Emergency Unblinding of Treatment Assignment

Emergency unblinding should only be undertaken when it is essential to treat the subject safely and efficaciously. Most often, test article discontinuation and knowledge of the possible treatment assignments are sufficient to treat a study subject who presents with an

emergency condition. It is encouraged for the investigator, when contemplating unblinding, to contact the sponsor or sponsor's designated Medical Monitor or designee to confirm the need to unblind, prior to unblinding (see [Section 2](#) for contact information). However, if required, the investigator can unblind without consulting the Medical Monitor.

Emergency code breaks are performed using the IxRS. When the investigator contacts the system to unblind a subject, he/she must provide the requested subject identifying information and confirm the necessity to unblind the subject. The investigator will then receive details of the drug treatment for the specified subject and a fax or e-mail confirming that the treatment assignment of the subject was unblinded. The system will automatically inform the sponsor's monitor for the site and the sponsor that the code has been broken.

It is the investigator's responsibility to ensure that there is a procedure in place at their site to allow access to the IxRS code break information in case of emergency. The investigator will inform the subject how to contact his/her backup in cases of emergency when he/she is unavailable. The investigator will provide protocol number, test article name if available, subject number, and instructions for contacting the sponsor (or any entity to which it has delegated responsibility for emergency code breaks) to the subject in case emergency unblinding is required at a time when the investigator and backup are unavailable.

All steps outlined above will be followed, including contacting the Medical Monitor as soon as possible and not more than 24 hours afterwards. It will be the responsibility of all study personnel to ensure that, except for the above procedure, investigator blinding is maintained until after study completion.

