### 8.17.5 Worsening or Progression of Disease Under Study

Worsening or progression of the qualifying pyelonephritis should be recorded as a clinical failure (as part of the efficacy assessment), rather than an AE, unless the worsening/progression also meets the criteria for a serious AE (in which case the event also should be reported as an SAE). In contrast, any new or secondary infections that the

investigator considers to be distinct from the qualifying pyelonephritis should be reported as AEs in all cases, whether non-serious or serious.

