#### b. Concomitant Antibiotic Therapy

Subjects who receive any systemic concomitant antibiotic therapy from the start of administration of the first dose of test article through the EOT visit (CE-EOT population), PTE visit (CE-PTE population) or FFU visit (CE-FFU population) that is potentially effective against the baseline pathogen, will be excluded from the CE population. If no pathogen is isolated and the systemic concomitant antibiotic is effective against Gram-negative uropathogens, the subject will be excluded from the respective CE population. Subjects who are a clinical failure on the particular visit and received non-study antibiotics for insufficient therapeutic effect of the test article, will not be excluded from the CE populations. Subjects who receive a systemic concomitant antibiotic that is not potentially effective against the baseline pathogen will be included in the CE populations.

c. Evaluable Success and Failure

Evaluable success: The subject received at least 3 doses of active test article and the investigator classifies the subject as a clinical success at the EOT visit (CE EOT population) or the overall clinical response (based on the investigator's assessment) at the PTE visit (CE-PTE population) or the overall clinical response (based on the investigator's assessment) at the FFU visit (CE-FFU population) is clinical success/cure.

Evaluable failure: The subject received at least 2 doses of active test article and the investigator classifies the subject as a clinical failure at the EOT visit (CE EOT population) or the overall clinical response (based on the investigator's assessment) at the PTE Visit (CE-PTE population) or the overall clinical response (based on the investigator's assessment) at the FFU visit (CE-FFU population) is clinical failure/relapse.

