#### 4.5 Microbiologically Evaluable Populations

The microbiologically evaluable (ME) population will include subjects in the CE and micro-ITT populations who have both an appropriately collected post-baseline urine sample and an interpretable post-baseline urine sample. An interpretable post-baseline urine culture is one that has a clearly identified pathogen or one where the baseline pathogen(s) can be excluded (ie, there is no growth of the baseline pathogen).

Since patient count may differ depending on timepoint, ME populations will be defined by milestone visit (ME-EOT and ME-PTE).

93 Version: 1.0 Status: Approved Approved Date: PTK0796-AP-17202 Statistical Analysis Plan

Omadacycline (PTK 0796)

Paratek Pharma, LLC

PTK0796-AP-17202 Statistical Analysis Plan

The ME populations consist of subjects in the micro-ITT population and the CE-EOT and CE-PTE populations, respectively who also have:

- A clean-catch urine specimen at the EOT and PTE visits, and
- Interpretable urine culture results at the EOT and PTE visits.

Subjects with an unfavorable microbiological outcome at EOT will be included in the ME-PTE population, regardless of whether they provide a urine culture at the PTE visit.

An interpretable post-baseline urine culture is one that has a clearly identified pathogen or one where the baseline pathogen(s) can be excluded (i.e., there is no growth of the baseline pathogen). A urine culture is considered uninterpretable if more than two bacterial isolates are identified, unless any of the following is observed:

- There is  $<10^4$  CFU/mL of the baseline pathogen(s), indicating eradication.
- There is  $\geq 10^4$  CFU/mL of the baseline pathogen(s), indicating persistence

At any visit after Screening, a pathogen the same species as the Baseline pathogen with a CFU count of  $\ge 1 \times 10^4$  CFU/mL should be considered a persisting pathogen.

At any visit after Screening, any culture with a CFU count of  $< 10^4$  CFU/mL should be considered a negative culture.

PTK0796-AP-17202 Statistical Analysis Plan

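### The CE blinding rule excuses a code break only for a treatment-limiting AE, so a subject unblinded for non-serious treatment failure is literally dropped from the CE and ME populations

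*SAP*

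**What the plan says.** SAP 4.4 lists the conditions for the CE populations under the instruction "Subjects must meet all of the following to be included in the CE populations". One of them is that "Study personnel involved in the assessment of efficacy remained blinded to study treatment, unless a treatment limiting AE occurred which required emergency unblinding". The condition carries no time limit and stands above the visit-specific criteria, so it governs all three sets: "CE populations will be defined by milestone visit (CE-EOT, CE-PTE and CE-FFU"). SAP 4.5 builds the ME populations on top of these: "The ME populations consist of subjects in the micro-ITT population and the CE-EOT and CE-PTE populations, respectively who also have" a suitable urine culture.

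Protocol 7.11 sets the ground for a code break in wider terms than an AE: "Emergency unblinding should only be undertaken when it is essential to treat the subject safely and efficaciously". Protocol 8.17.5 says how a failing infection is recorded: "Worsening or progression of the qualifying pyelonephritis should be recorded as a clinical failure (as part of the efficacy assessment), rather than an AE", with the exception that worsening which meets the seriousness criteria is also reported as an SAE.

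Elsewhere SAP 4.4 takes care to keep failures evaluable. Item 3b does not exclude from CE "Subjects who are a clinical failure on the particular visit and received non-study antibiotics for insufficient therapeutic effect of the test article". Item 3c asks for 2 active doses for an evaluable failure, against 3 for an evaluable success. A clinical failure at EOT is exempt from the PTE visit window. No matching sentence covers a failure whose code was broken.

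**The concern.** The waiver reaches tolerability but not lack of effect. A subject who stops for an AE and is unblinded because of it stays in CE. A subject who stops because the infection is not responding, and is unblinded for that reason without an SAE, does not. Membership in CE and ME then depends on the outcome those populations are meant to measure.

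Blinding is required so that knowledge of the arm cannot colour the efficacy judgement. That purpose is not served by removing a subject whose failure was already on record when the code was broken.

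What is at stake is the CE and ME clinical success rates. SAP 7.2.1 repeats its analysis in these populations, including the posterior probability that omadacycline is within 10 points of levofloxacin.

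**Working it through.** **Step 1. Follow one subject through the rules.** Take a subject with non-serious worsening who is judged a clinical failure at EOT, has had at least 2 active doses, is given another antibiotic, and whose code is then broken.

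| Rule | Result |
|---|---|
| SAP 4.4 item 3b, other antibiotics | stays in |
| SAP 4.4 item 3c, minimum doses | evaluable failure |
| SAP 4.4 PTE window, EOT failures exempt | stays in CE-PTE |
| SAP 8.2 compliance, expected doses counted only to the last dose date | early stopping does not itself breach 80% |
| SAP Table 5, failure at EOT | failure at PTE whatever follows |
| SAP 4.4 item 2, blinding; protocol 8.17.5, no AE recorded | **excluded** |

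The criteria are cumulative, so the last row decides. Because ME requires CE, she also leaves ME-EOT and ME-PTE. If the worsening is an SAE, an AE exists and the waiver can apply. Protocol 8.13 makes prolonged hospitalization sufficient for seriousness.

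**Step 2. Effect on one arm's rate.** SAP 7.1.1.2 defines CE clinical success as successes/(successes + failures). With s successes among n subjects, dropping k failures changes the rate by

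s/(n − k) − s/n = s·k / [n(n − k)],

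which is positive for every k ≥ 1 when s > 0. The documents give neither k nor the CE size per arm. Assume n = 30, the per-group size used in SAP 3.1 (stated there for micro-ITT), and k from 0 to 2.

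| Successes of 30 | k = 0 | k = 1 | k = 2 |
|---|---|---|---|
| 24 | 80.0% | 24/29 = 82.8% (+2.8) | 24/28 = 85.7% (+5.7) |
| 23 | 76.7% | 23/29 = 79.3% (+2.6) | 23/28 = 82.1% (+5.5) |
| 21 | 70.0% | 21/29 = 72.4% (+2.4) | 21/28 = 75.0% (+5.0) |

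The lower two rows lie near the 0.78 and 0.69 rates assumed in SAP 3.1. These are shifts in one arm's rate and should not be read directly against the 10-point margin, which applies to a difference between arms.

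**Step 3. Effect on the comparison.** SAP 7.2.1 uses P(p_OMC − p_L > −0.1 | data) with Beta(0.5, 0.5) priors; the target in SAP 3.1 is 0.70. To check the calculation, I reproduced the plan's stated probabilities of reaching that target with equal true rates, by exact enumeration:

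| True rate, N per group | Stated | Recomputed |
|---|---|---|
| 0.69, 30 | 65% | 66.2% |
| 0.69, 80 | 80% | 80.5% |
| 0.78, 30 | 68% | 68.1% |
| 0.78, 64 | 80% | 80.8% |

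The same posterior, for an assumed result of 19/30 on omadacycline and 21/30 on levofloxacin:

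| Failures dropped (OMC, LEV) | Posterior |
|---|---|
| 0, 0 | 0.616 |
| 1, 0 | 0.682 |
| 2, 0 | 0.747 |
| 1, 1 | 0.610 |
| 2, 2 | 0.603 |

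Two losses confined to the omadacycline arm carry this example across 0.70. Equal losses barely move it, and here slightly lower it.

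**The case against.** The strongest reply is that almost nobody meets the description. Protocol 7.10 confines unblinding to subject emergencies and the end of the study. Protocol 7.11 requires that the break be essential, and its reference to treating safely and efficaciously can be read as one joint test. It also expects breaks to be seldom needed: "Most often, test article discontinuation and knowledge of the possible treatment assignments are sufficient to treat a study subject who presents with an" emergency. Ordinary failures have a route without a code break, since under protocol 7.14 test article stops and further treatment is at the discretion of the investigator or the subject's health care provider. Worsening grave enough to be an emergency, in subjects who should be in hospital, will often be an SAE and so can come within the waiver. All of this stands. It limits how often the rule bites, without changing what the rule says when it does.

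It can also be argued that a failure judged blind at EOT satisfies the criterion for that assessment, and that the Pathogen and CE Review Plan may settle the matter. That plan is not among the documents. SAP 4.4 states the condition without a time limit and as mandatory, so the reasonable reading should be written down.

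Items 3b and 3c do not contradict item 2. They govern other matters, and a subject can pass them and still fail the blinding condition. What can be said is that item 2 departs from the section's evident intention to keep failures evaluable.

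A reader might infer that the rule favours the weakest regimen and narrows the gap to levofloxacin. The documents do not support that. Nothing indicates that such code breaks would differ by arm, and the worst failures are the ones most likely to be SAEs and hence able to stay in. Nor is failure the only non-AE route out: protocol 8.15 allows an assignment look-up after an overdose, whatever the outcome.

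**Conclusion.** The gap in SAP 4.4 item 2 is real, and its severity is minor. As written, it excludes subjects unblinded for non-serious treatment failure from all CE and ME populations, and each exclusion can only raise the clinical success rate of that arm. With 30 evaluable subjects and 24 successes the rise is 2.8 points for one case and 5.7 for two. Both the counts and the arm size are assumptions, and with no such case there is no effect.

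It would go too far to conclude that every subject unblinded for a failing infection is lost, or that the trial's success rates are overstated. SAE-level worsening can be waived. ITT and micro-ITT, the latter being the protocol's primary population, have no blinding criterion and keep these subjects. SAP 7.1 treats all efficacy endpoints as exploratory. The comparison with levofloxacin is at risk only if losses are unequal between arms.

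**What to change.** Amend SAP 4.4 item 2, and the Pathogen and CE Review Plan to match, to say that:

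- the blinding criterion applies up to the efficacy assessment that defines the population in question;
- the existing waiver for a treatment-limiting AE remains;
- a subject recorded as a clinical failure, or with test article stopped for insufficient effect, before the code break stays in CE, and in ME if its other criteria are met, as an evaluable failure;
- a code break that precedes any recorded failure still leads to exclusion.

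Reporting code breaks by arm and reason would show whether the rule mattered.

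The cost is a sentence or two, settled before unblinding. The small downside is the need to compare the IxRS code-break record with the recorded failure or stop decision. Protocol 8.19 specifies only a date for stopping, so the order of events on the same day would have to be settled from source documents during the blinded CE review. That needs the timing of the break, not the treatment it revealed.
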